Study participants (n=54) will be reimbursed \$30 for completing each assessment visit (including in-person visit, blood draw at Quest, and wearing/returning the research activity monitor). They will also be reimbursed of up to \$9 for parking- for each visit. These visits will take place at baseline, 6 and 12 months. Participants will also receive an incentive gift, valued at \$15, for completing their 6-month follow-up visit within their 2-week window. Participants completing their 12-month follow-up visit will receive an incentive of being able to keep the activity monitor provided to them as part of the intervention (valued at \$100-150) and will receive an incentive gift, valued at \$15, for completing their 12-month follow-up visit within their 2-week window.

5. Recruitment materials: (attach all material to be seen or heard by subjects, including advertisements and scripts)

Study Aims

1. * Describe the purpose, specific aims, or objectives and state the hypotheses to be tested:

The majority of US adults report lower than recommended physical activity (PA) levels.[1] Clinical guidelines from the American Heart Association (AHA), the American Diabetes Association (ADA), and the US Preventive Services Task Force (USPSTF) endorse physical activity for treating common cardiometabolic health conditions including obesity, dyslipidemia, and hypertension. [2-5] Although, clinical advice has been shown to positively affect lifestyle behaviors,[6,7] referral to physical activity by health professionals is relatively new and not part of standard care.[8-11]

Aim: To evaluate an intervention program for physical activity improvement in adult primary care patients with cardiometabolic risk factors. Primary care patients will be recruited (n=54) and randomized to receive a body worn physical activity monitor (PAT) alone or a PAT and ActiveGOALS (v2). The ActiveGOALS core program (uses paper and online tracking; IRB STUDY19080212) is currently being evaluated for use in the general adult clinical population (randomized control trial with 3 month end-point). This new effort will determine success of an updated (v2) core program with integrated use of a body worn monitor as a behavior change tool plus a 9 month maintenance program. Outcomes will be assessed at baseline, 6, and 12 months.

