- I bring a novel skill set to this research. The additional training received through this K01 will uniquely position me to lead future efforts leveraging available technologies and clinical resources toward developing feasible programs for physical activity referral. I have an in-depth knowledge of body-worn PATs and a strong foundation in public health research. Through my K12, I acquired knowledge of Patient-Centered Outcomes Research. K01 funding will enable me to receive the training an experience that would enable me to utilize quantitative methods when involving stakeholders, to gain expertise in the use of EHR data in assessing clinically-integrated interventions, and to learn how to best utilize PAT output to

encourage behavior change. Process development strategies and pilot intervention data acquired during the K01 will be essential to being able to move forward in my own unique career trajectory.

Study Design

1. Total number of subjects to be enrolled at this site (enter -1 for chart reviews, banking, registries):

54 to undergo research procedures; 200 to undergo screening

2. Describe and explain the study design:

Fifty-four participants will be randomized to one of two groups: physical activity tracker (PAT)+ActiveGOALSV2 or the active control: PAT only.

3. Describe the primary and secondary study endpoints:

1. Average Step Counts per day
2. % of participants achieving the 150 minute/week aerobic activity goal

Secondary: changes in body weight, waist circumference, blood pressure, glycemic control (fasting blood glucose and hba1c), and cholesterol (ldl, hdl, triglycerides) from study collected clinical outcomes. Quality of life and PROMIS score from health questionnaire.

4. Provide a description of the following study timelines:

Duration of an individual subject's active participation:

12-15 months

Duration anticipated to enroll all subjects:

12 month enrollment period

Estimated date for the investigator to complete this study (complete primary analyses):

12/31/2022

5. List the inclusion criteria:

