*** Identify the subgroups and provide a justification:**

Children are excluded. The physical activity requirements of 150 minutes of physical activity pertain only to adults. The intervention is designed for adults- materials specific to children would have to be designed for children.

8. Describe the power analysis used and cite your method of statistical analysis.

If a power analysis is not possible, thoroughly justify the sample size required for the study, including appropriate literature citation (alternatively provide page reference in attached protocol):

For our Aim 1a primary outcomes, we hypothesize that participants randomized to ActiveGOALSV2 + PAT will have significantly larger (a) increases in step counts/day and % meeting moderate-vigorous physical activity goal of 150 minutes/week (to 12 months) compared to the active PAT control group. Descriptive analyses and graphic displays will be used to identify outliers, missing data, and pattern of attrition. To ensure rigor, the primary analytic strategy will be a linear or generalized mixed-effect models approach in which treatment group, time, and time by group interaction are treated as fixed effects, and subject is treated as a random effect to account for individual subject variability (two sided hypothesis test; .05 level). Mixed models are applicable to longitudinal datasets that contain missing observations, (assuming data is missing at random). Regression modeling will be conducted to adjust for important covariates. We will perform similar analyses to examine changes in secondary outcomes. Descriptive statistics on patient experience, beliefs/attitudes related to maintenance of physical activity changes, and program cost will also be reported.

Power and sample size: For a 2 sided test with alpha level set at .05, and assuming 20% attrition at 12 months, we plan to recruit 54 participants to identify clinically relevant mean difference between randomized groups at 12-months of 2000 steps/day (with a power of .80), and 35% meeting MVPA goal (with a power of .80), given reference mean (sd) values were calculated from baseline waist worn accelerometer data from the current K12 of: 5250 (2200) steps/ day and we assume 5% meeting goal at baseline in the control group.

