Coverpage

Title: Advancement of Clinical Referral to Physical Activity for Cardiometabolic Disease Prevention

Brief Title: The Clinical Referral to Activity Study

NCT: NCT04743856

Date Created/Modified: November 3, 2025

Statistical Analyses

6.1.6 Statistical Analyses: For our primary outcomes, we hypothesize that participants randomized to ActiveGOALSV2 + PAT will have significantly larger (a) increases in step counts/day and % meeting MVPA goal of 150 minutes/week (to 12 months) compared to the active PAT control group. Descriptive analyses and graphic displays will be used to identify outliers, missing data, and pattern of attrition. To ensure rigor, the primary analytic strategy will be a linear or generalized mixed-effect models approach in which treatment group, time, and time by group interaction are treated as fixed effects, and subject is treated as a random effect to account for individual subject variability (two sided hypothesis test; .05 level). Mixed models are applicable to longitudinal datasets that contain missing observations, (assuming data is missing at random). Regression modeling will be conducted to adjust for important covariates. We will perform similar analyses to examine changes in secondary outcomes. Descriptive statistics on patient experience, beliefs/attitudes related to maintenance of PA changes, and program cost will also be reported. Mixed models are used to help account for missing data and no adjustments will be made for multiple comparisons.

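### The SAP names no test statistic and no empty-cell method for the activity-goal outcome; on the plan's own planning rates a Wald test would have about 0.49 power against the stated 0.80

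*SAP*

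**What the plan says.** SAP 6.1.6, and the matching text in the protocol's Study Design item 8, give one analysis for both primary outcomes: "a linear or generalized mixed-effect models approach in which treatment group, time, and time by group interaction are treated as fixed effects", with a random subject effect and two-sided testing at 0.05. Percent meeting the activity goal is binary, so the generalized branch applies to it. Neither document names the link, the estimation method, the coding of time or the test statistic, and neither says what happens if no one in an arm meets the goal at a visit.

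The planning figures are in Study Design item 8: "For a 2 sided test with alpha level set at .05, and assuming 20% attrition at 12 months, we plan to recruit 54 participants". The goal effect is "35% meeting MVPA goal (with a power of .80", and for the control rate "we assume 5% meeting goal at baseline in the control group". No 12-month control rate is given. Study Aims item 1 sets the visits: "Outcomes will be assessed at baseline, 6, and 12 months".

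**The concern.** A 5% rate in about 22 people means about one expected achiever (22 × 0.05 = 1.1), so none at all is a likely result. If each arm and visit has its own parameter and the model is fitted by ordinary maximum likelihood, an empty control cell at 12 months sends the log odds ratio to infinity. Its standard error grows without limit as well, and the Wald p-value moves towards 1. The trials most likely to show this are those with a clear effect, such as 0/22 against 9/22.

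At stake is the stated 0.80 power for one of two primary outcomes. The documents leave open a choice that moves power by more than 35 points on the plan's own rates. Making that choice after an empty cell has been seen would be post hoc.

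**Working it through.** **Inputs.** 54 randomised (Study Design item 2); two-sided 0.05, 20% attrition, a 35% goal effect and a 5% control rate (Study Design item 8). Assumed: 1:1 allocation, since no ratio is stated. Completers: 54 × 0.8 = 43.2, or 21 to 22 per arm.

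**Reproducing the plan's N.**
- Steps/day: a two-sample t-test for a difference of 2000 with SD 2200 needs 21 per arm; 21/0.8 = 26.25, so 27 per arm, or 54.
- Goal, 5% against 40%, with n = [1.96√(2p̄q̄) + 0.8416√(p₁q₁ + p₂q₂)]² / d². Here p̄ = 0.225 and d = 0.35: (1.96 × 0.5906 + 0.8416 × 0.5362)² / 0.1225 = 2.588/0.1225 = 21.1, so 22 per arm. 44/0.8 = 55, within 2 of 54. Power at 21 to 22 per arm is 0.797 to 0.817.
- Goal, 5% against 35% (the other reading): 27 per arm; 54/0.8 = 67.5, so 68. This does not reproduce.

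So the stated N fits this outcome only when 5% is used as the 12-month control rate against 40%.

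**Chance of an empty control cell at 12 months.** 0.95²² = 0.324 (0.95²¹ = 0.341), about one trial in three.

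**Power at 12 months.** All 2×2 tables were enumerated with 22 per arm, in a logistic model with arm only, at 5% against 40%:
- No control achiever (probability 0.324): Wald rejects with probability 0, likelihood ratio with probability 0.998.
- At least one control achiever (0.676): Wald 0.731, likelihood ratio 0.801.
- Overall Wald: 0.676 × 0.731 = 0.494. Overall likelihood ratio: 0.324 × 0.998 + 0.676 × 0.801 = 0.865.
- Firth-penalised likelihood ratio 0.86, score test 0.86, Fisher 0.77.

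Two small simulations of a random-intercept logistic model with categorical time (assumed random-effect SDs between 0.5 and 2) agree. At these rates Wald power was 0.42 to 0.51, and likelihood-ratio power was 0.87 in the one that computed it.

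**Sensitivity, 22 per arm.**

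| Control / active at 12 months | P(no control achiever) | Wald | Likelihood ratio |
|---|---|---|---|
| 5% / 40% | 0.32 | 0.49 | 0.865 |
| 5% / 35% | 0.32 | 0.39 | 0.77 |
| 10% / 45% | 0.10 | 0.64 | 0.80 |
| 15% / 50% | 0.03 | 0.66 | 0.75 |

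**Type I error, same enumeration.** The plain likelihood-ratio test reaches about 0.08 when both arms are at 10%. The Firth test stays at or below about 0.05 for common rates from 5% to 40%. Naming the plain likelihood-ratio test would therefore restore power but not hold the level.

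**Illustration, 0/22 against 9/22.** The maximum-likelihood odds ratio is infinite and the Wald test is not significant. The likelihood-ratio p is about 0.0001, and the profile interval for the odds ratio runs from about 6.4 with no upper limit. The risk difference is 9/22 = 41 points, with Newcombe 95% interval about 18 to 61. The Firth odds ratio (add 0.5 to each cell) is (9.5/13.5)/(0.5/22.5) = 31.7.

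**The case against.** The strongest reply is that the documents do not say Wald, categorical time or ordinary maximum likelihood. That is right. With time entered linearly, a zero at 12 months alone does not make the estimate diverge, and the same likelihood with a likelihood-ratio test has 0.865 power. A reader might infer that the stated model fails to deliver 0.80; the text supports only that it may or may not, depending on choices it leaves open.

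The second reply is that 5% is a baseline rate, and that controls receive a tracker and activity advice that may raise it. This also stands in part. At a 10% or 15% control rate empty cells become uncommon and the Wald penalty falls to 16 or 9 points. But 5% is the only control rate given, and the sample size works for this outcome only if it persists to 12 months.

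Three further inferences are tempting and should not be drawn:
- *The problem arises on any effect scale.* It does not. The outcome is defined as a percentage, and a difference in percentages is finite with an empty cell.
- *Nothing could be reported.* The 0/22 against 9/22 example shows otherwise: the risk difference has a two-sided interval and the odds ratio a finite lower limit.
- *Empty cells at any visit count.* At 5%, the chance that at least one arm has 0 of 27 at baseline is 1 − (1 − 0.95²⁷)² = 0.44, and the simulated chance of any empty arm-by-visit cell is about 0.70. Neither bears on a named 12-month between-arm contrast. Baseline zeros would matter if the tested term were the change from baseline, which the documents do not settle.

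**Conclusion.** The point holds as a gap in specification with a measurable cost. On the rates that reproduce the sample size (5% against 40%, 1:1, about 22 completers per arm), about one trial in three would have no control achiever at 12 months. Reading a Wald test from an ordinary maximum-likelihood fit with categorical time would then give about 0.49 power in place of 0.80. A penalised likelihood-ratio test recovers about 0.86 from the same data while holding the level, so the data carry the information and the choice of test decides whether it is used.

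The size depends on the 12-month control rate, which the protocol does not state: the Wald shortfall against likelihood ratio is 37 points at 5%, 16 at 10% and 9 at 15%. The exact figures are for a simple 12-month logistic model; the mixed-model figures are approximate. The steps/day outcome is unaffected. This should be settled before analysis, but it does not invalidate the design.

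**What to change.** In SAP 6.1.6, and in the matching protocol text:

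1. Keep the generalized mixed model as the primary analysis of the goal outcome, so that the 6-month data and the missing-at-random handling are retained under 20% expected attrition. State how time is coded.
2. State that this outcome is fitted by penalised estimation (Firth-type, or a weakly informative prior), whether or not a cell turns out to be empty.
3. Name the 12-month between-arm contrast as the tested quantity, and test it by penalised likelihood ratio, not Wald.
4. Report the 12-month difference in percent meeting the goal with a Newcombe interval, beside the odds ratio.
5. Add Firth logistic regression at 12 months as a sensitivity analysis. It should not replace the mixed model, because it uses only participants with 12-month data.
6. State the control rate assumed at 12 months and whether the 35% is a difference or a rate.

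The cost is SAP wording, a little more programming and slight shrinkage of the odds ratio. No change to sample size or data collection is needed.

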Brief weekly motivational feedback from a coach (with a physical activity and health or exercise science background) will be provided during the 13 week “core” intervention program via the ActiveGOALSV2 platform. Coaches will also access study administered participant PAT accounts. The coach will set goals in the PAT program to match weekly study goals and will utilize other program features (like reminders and push messaging) according to protocol developed in yr 1 of funding).

The primary behavior tracking tool will be a wrist worn PAT. However, participants will also be provided with paper and online tracking tools for physical activity to track/ report their step counts and activity minutes. I am currently working with Fitbit® monitors in other clinical patient population studies which we plan to use in this study. Currently, Fitbit devices are the most commonly used brand in the US and have been shown to validly and reliably record step counts.[69,70] As done in other studies, we will set-up PAT accounts for participants.

Outcome Assessment: All outcome measures will be collected at all time points (baseline, 6 and 12 months post-intervention) for all participants. After being consented, physical activity levels, clinical, and questionnaire measures will be

collected. Clinic visits should take 30-45 minutes to complete. Blood draws will be performed at a Quest™ lab.

Primary outcomes: Average step counts/day and time spent in moderate-vigorous (MV) physical activity will be collected from validated research grade body-worn PATs; ActiGraph wGT3X+ accelerometer (ActiGraph LLC; Pensaco-la, FL) worn on the waist during waking hours for the 7 days after a clinic visit. These accelerometers have been validated for assessing time spent in physical activity intensities and step counts in laboratory[76-81] and field settings[80,82-84] and are used to validate commercial monitors.[69,70] Data recorded in 1 second epochs will be output as activity counts [85,86] and converted to step counts and time spent in MV physical activity using accepted cut-points.[78,86]

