Participants will be given a monitor and instructions (verbal, paper, and online video). Monitors will be returned by mail. Monitor on/off times will be reported via diary. To reduce reactivity, the first day of monitor data will not be used. Four or more days with at least 10 hours of wear/ day will be required for a record to be valid. Participants with incomplete data will be given the opportunity to “rewear” the monitor for a given visit (we expect <8% to require monitor rewear for any given visit; based on previous studies).

Secondary outcomes: Secondary analyses may not be fully powered (at $p<0.05$), but the findings will inform the design of an R01, fully-powered to examine the effect of ActiveGOALSV2 on cardiometabolic outcomes. Height (w/ stadiometer), weight (w/ electronic scale), waist circumference, and blood pressure (w/ automatic cuff) will be taken using validated instruments/techniques employed in previous GLB studies.

Weight: Weight will be measured twice without shoes on using a portable scale placed on a hard, flat surface. The subject will be asked to stand in the middle of the scale without touching any surface with eyes straight ahead. The subject will be asked to step down from the scale between measures. If the measures are more than 0.5 pounds apart, a third measure will be taken.

Height: Height will be measured twice without shoes. The subject will be asked to stand erect under the stadiometer with eyes straight ahead. Subjects will be asked to step down between measures. If the measures are more than one-half inch apart, a third measure will be taken.

Blood Pressure: Blood pressure will be measured with a validated automated cuff in the right arm with the patient seated comfortably with the right arm resting on a table. Participants will be asked to rest quietly with feet flat on the floor for five minutes. The cuffed arm will be raised for 5 seconds after each inflation and a wait of 30 seconds will occur between each blood pressure reading. Blood pressure will be repeated twice with the average computed. If it is not possible to measure blood pressure in the right arm, the left arm should be utilized and noted in the patient record.

Waist Circumference: The participant should be wearing loose clothing and standing

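### The step-count model does not commit to adjusting for baseline steps, so its implied 12-month contrast is valid but usually less precise than it could be

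*SAP*

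**What the plan says.** SAP 6.1.6 and Protocol, Study Design item 8, give the same primary model: a "linear or generalized mixed-effect models approach in which treatment group, time, and time by group interaction are treated as fixed effects", plus a random subject effect. The hypothesis concerns larger increases in daily steps, up to 12 months, in the intervention arm. Under Research Activities, Outcome Assessment, the Protocol states: "All outcome measures will be collected at all time points (baseline, 6 and 12 months post-intervention) for all participants".

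The only wording on adjustment is "Regression modeling will be conducted to adjust for important covariates"; no covariate is named. On incomplete records the SAP says "Mixed models are used to help account for missing data".

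Protocol item 8 sizes the step outcome on a "clinically relevant mean difference between randomized groups at 12-months of 2000 steps/day", "assuming 20% attrition at 12 months, we plan to recruit 54 participants", with "reference mean (sd) values were calculated from baseline waist worn accelerometer data from the current K12 of: 5250 (2200) steps/ day". That SD describes baseline levels. No SD of change and no correlation between visits is given.

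**The concern.** The model uses baseline steps as an outcome row but leaves the baseline difference between arms free. The 12-month interaction term therefore subtracts the observed baseline imbalance in full. Randomisation makes the true imbalance zero, so part of what is subtracted is noise. With 27 per arm (1:1 allocation assumed, since no ratio is stated) and SD 2200, the standard error of that imbalance is 2200 × √(2/27) = 599 steps/day, about 30% of the 2000-step target.

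An analysis that adjusts for baseline, by a covariate or by a common baseline mean, removes only the part that predicts follow-up. At stake is precision in a trial of 54 people with 20% expected attrition. Validity is not in question. The plan also leaves unstated which contrast is the primary test.

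**Working it through.** **Inputs.** From Protocol item 8: difference 2000, SD 2200, N = 54, 20% attrition, two-sided .05, power .80. Assumed: 27 per arm; correlation ρ between any two visits of .3 to .8; half of those missing at 12 months are seen at 6 months.

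**The plan's own figure.** Steps, normal approximation: 2 × (1.960 + 0.842)² × (2200/2000)² = 19 per arm, or 38, and 38/.8 gives 48. A t-test needs 20 per arm, and 40/.8 = 50. The activity-goal outcome read as 5% against 40% needs 22 per arm, and 44/.8 = 55, close to 54. So the binary outcome appears to drive N. With 54 × .8 ≈ 43 completers, a t-test of 12-month step levels has power .83.

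**What the interaction term estimates.** With complete data it is the difference in mean changes. A random-intercept fit to one simulated complete data set gave 2367.98 for both.

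**Complete data, equal SDs.** Variance per person:
- change: 2·SD²·(1 − ρ)
- baseline-adjusted: SD²·(1 − ρ²)
- ratio adjusted/change: (1 + ρ)/2, which is .65 at ρ = .3, .75 at .5 and .85 at .7

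**With dropout.** Generalised least squares over three visits, 27 per arm, 5.4 per arm missing at 12 months, covariance treated as known, noncentral t with 52 df:

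| ρ | SE change | SE adjusted | Variance ratio | Extra participants for change | Power change | Power adjusted |
|---|---|---|---|---|---|---|
| .3 | 762 | 637 | .698 | 43% | .731 | .869 |
| .4 | 709 | 611 | .743 | 35% | .791 | .895 |
| .5 | 649 | 576 | .787 | 27% | .856 | .926 |
| .6 | 583 | 531 | .831 | 20% | .920 | .959 |
| .7 | 506 | 474 | .874 | 14% | .972 | .986 |
| .8 | 415 | 397 | .917 | 9% | .997 | .999 |

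The extra-participant column is 1/ratio − 1. The difference detectable with .80 power is 2176 (change) against 1818 (adjusted) steps/day at ρ = .3, 1854 against 1645 at .5, and 1446 against 1352 at .7. Change-contrast power equals .80 at ρ = .414. That threshold runs from .402 to .425 over 41 to 82 df and 0 to 100% of the missing being seen at 6 months.

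**If spread grows after baseline.** Let follow-up SD be k times baseline SD. With complete data the change variance exceeds the adjusted variance by SD²·(1 − kρ)², which is never negative and is zero at ρ = 1/k. For k = 1.3 (assumed), with dropout, power at ρ = .3/.4/.5/.6/.7/.8 is:
- change: .583/.642/.714/.797/.888/.967
- adjusted: .660/.696/.746/.811/.890/.967

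Power crosses .80 at ρ = .603 (change) and .585 (adjusted).

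**Cost of estimating the covariance.** In 8,000 simulated trials per case with dropout, an unstructured covariance was estimated for both contrasts. At ρ = .3/.5/.7:

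| | SE change | SE adjusted | Variance ratio |
|---|---|---|---|
| Equal SDs | 760/648/514 | 634/583/486 | .70/.81/.89 |
| Follow-up SD 1.3 × baseline | 917/780/629 | 849/757/632 | .86/.94/1.01 |

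Mean estimates were 1992 to 2024 against a true 2000. With equal SDs the simulated SEs lie within about 3% of the known-covariance values above (largest gap 486 against 474).

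**The case against.** The planned model is standard, unbiased and matches a hypothesis about increases. Both facts stand; this is a matter of efficiency.

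The gain depends on a correlation that the documents do not give, and it may be slight. At ρ = .8 the power difference is .002, and with follow-up SD 1.3 times baseline the two contrasts are about equal from ρ = .7 up. This stands too, and it limits the size claimed. It gives no reason to prefer the change contrast, since adjustment is at worst about equal.

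Steps are not the outcome that appears to set N, and the remedy does nothing for the activity goal. Correct.

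The sentence on important covariates could cover baseline steps. It permits that adjustment but does not fix it, so the choice could be made after the data are seen.

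An unstructured covariance and small-sample degrees of freedom may look like more than the gap requires. A baseline covariate with 6 and 12 months as outcomes would also close it. The unstructured form is suggested because it protects the common-baseline model when variances differ between visits. The simulations did not fit the plan's random-intercept model or check the size of a Kenward-Roger test; they show only that estimating the larger covariance costs little precision.

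**Conclusion.** The concern holds. The plan does not commit to baseline adjustment for steps, and the contrast it implies is valid but usually less precise than one that adjusts. With equal SDs and the assumed dropout, adjustment cuts the variance by 30% at ρ = .3, 21% at .5, 13% at .7 and 8% at .8. The change contrast falls below .80 power only if ρ is below roughly .40 to .42, so no shortfall against the plan's target is shown. If follow-up SD is 1.3 times baseline, the benefit largely disappears from ρ = .7, and both analyses are under .80 below ρ of about .58. The correlation, SD ratio, allocation and dropout pattern are all assumptions.

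**What to change.** For steps/day only, state that the primary test is the single-degree-of-freedom difference between arms at 12 months, adjusted for baseline steps, from one named model. A suitable one is a mixed model with:
- categorical time (baseline, 6 and 12 months);
- one baseline mean common to both arms, and group effects at 6 and 12 months;
- unstructured covariance across the three visits;
- small-sample degrees of freedom, such as Kenward-Roger.

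Make the 6-month contrast secondary.

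The cost is SAP wording and six covariance parameters in place of two; no new data are needed. This model also keeps anyone without a valid baseline record, which should be rare: the Protocol offers a repeat wear and says "we expect <8% to require monitor rewear for any given visit".

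Timing matters. Protocol, Study Design item 4, estimates completion of primary analyses at 12/31/2022, and both documents are dated November 3, 2025; they do not say whether outcomes have been examined. If they have, keep the planned model as primary, report the adjusted analysis beside it, and label it as specified afterwards.
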